9.7. Data analysis

Detailed methodology for summary and statistical analyses of data collected in this study will be documented in a separate statistical analysis plan (SAP), which will be dated, filed and maintained by the sponsor. The SAP may modify the plans outlined in the protocol; any major modifications of primary endpoint definitions or their analyses would be reflected in a protocol amendment.

Analyses will be performed by pH Associates using Stata (StataCorp LLC) and R. Data from all participating centres will be pooled for analysis.

According to the objectives, descriptive statistics will be presented using data at 1 year (using retrospective data collected) or 2 and 3 years (using the prospective data as well as the retrospective data collected) following initiation of palbociclib. Clinical measurements will be presented at each time-point available, as described in section 7.3. The interim study report will only present results for objectives which are relevant to the 1-year follow-up period and the final report will present results for objectives which are relevant up to the 3-year follow-up period.

Descriptive statistics (numbers, percentages, means, standard deviations [SD], medians, quartiles, minimum, and maximum), as appropriate to the data collected, will be used to describe baseline demographic and clinical characteristics for the overall study. Treatment patterns and hospital admissions will also be reported using descriptive statistics. The frequency and proportion of patients experiencing a neutropenia, febrile neutropenia event;

and gastro-intestinal toxicity including diarrhea, nausea and vomiting, during follow-up, will be presented.

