Calcium levels to be extracted at pre-first cycle, then at each cycle, in the first year following initiation	✓	✓	✓	
Phosphate levels to be extracted as above	✓	✓	✓	
Calls from patient to CNS: dates and reason			✓	
BC-related inpatient admissions to hospital: planned (elective), A&E, reasons, duration (dates of entry and discharge)			✓	
BC-related outpatient admission: dates, reason			✓	

Variables	Study time points			
	Baseline (From disease diagnosis to index date)	Index date	Post- initiation observatio n period	Other
Progression: sites, dates			✓	
AE: Neutropenia (Y/N), date start and end, grade			✓	
AE: Febrile Neutropenia (Y/N), date start and end			✓	
AE: Diarrhoea (Y/N), date start and end, grade			✓	
AE: Nausea (Y/N), date start and end, grade			✓	
AE: Vomiting (Y/N), date start and end, grade			✓	
Death: date, cause				✓

Note: All dates are DD/MM/YYYY for all patients, except for date of birth (MM/YY)

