2.1 STUDY DESIGN

This study will be a UK-wide, multi-centre, non-interventional cohort study (Figure 1). The study will involve secondary use of hospital medical records (paper-based or electronic, as appropriate), collected both retrospectively and prospectively, from patients' medical records. Data will be collected for a maximum of 3 years following enrolment into the IPP.

The palbociclib initiation date will be defined as the index date. The baseline period will extend from the date of diagnosis up to palbociclib initiation (index date). The post-initiation observation period will be defined as the period from the index date until the end of the 3-year follow-up period. Patients will contribute data up to the time that they are lost to follow-up (for example due to discharge, death, or other reasons) or 3-year post-index observation period, whichever is sooner.

PFIZER CONFIDENTIAL

[figure not shown]
[figure not shown]

Figure 1. Schematic of study design**Study population**

Across the entire UK, 846 women received palbociclib as part of the IPP. In the sites selected for this study, approximately 200 patients received palbociclib as part of the IPP and consented to participate in the study.

All patients meeting the following eligibility criteria will be included in the study:

- Patients enrolled into the IPP at one of the selected sites.
- Patients who received ≥ 1 dose of palbociclib as part of the IPP at one of the selected sites.
- For sites where data collection is performed by pH Associates, written informed consent will be required from living patients to access their medical records.
- Patient aged ≥ 18 years old at enrolment into the IPP

All eligible patients within the selected sites will be recruited into the study (and who provide informed consent, in the case of living patients, at sites where data collection is performed by pH Associates).

Data will be retrospectively collected from the point of patient's enrolment into the IPP until initial data collection, expected to take place between November 2018 and February 2019. After the initial retrospective data collection, data will be collected prospectively up to a maximum of 3 years from enrolment in the IPP by members of the direct care team by updating the eCRF with any subsequent therapeutic and progression data available in the medical records until the end of the 3-year follow-up period.

PFIZER CONFIDENTIAL

Data source

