 - Number of lines of prior chemotherapy for metastatic disease
 - Proportion of patients for whom an LHRH was used
 - Proportion of patients treated with endocrine therapy in the neoadjuvant or adjuvant setting
 - Endocrine therapy name
 - Proportion of patients treated with endocrine therapy in the advanced/disease modifying/metastatic setting
 - Endocrine therapy name
 - Number of lines of prior endocrine therapy for metastatic disease
- Proportion of patients treated with radiotherapy in the advanced/disease modifying/metastatic setting
- Concomitant medications (defined as medications prescribed whilst on palbociclib)
- Concomitant medications prescribed alongside goserelin

PFIZER CONFIDENTIAL

- Number of prior treatments in the metastatic setting, all prior therapies as well as chemotherapy/endocrine therapy combined and separately

[figure not shown]
Secondary Objective 1: To describe treatment pattern (as per licence/IPP requirement); including the proportion of patients with dose modification and who switch treatment 1, 2 and 3 years after palbociclib initiation, and median time to dose modification and treatment discontinuation ('drug survival'). For patients who progress, to describe the 1st /2nd /3rd line of treatment after progression.

- Summary measures of palbociclib treatment patterns including:
 - Starting Dose.
 - Endocrine partner prescribed alongside palbociclib
 - Proportion of patients with dose reductions at 1, 2 and 3 years after initiation.
 - Proportion of patients with palbociclib treatment discontinuation at 1, 2 and 3 years after initiation.
 - Reasons for discontinuation of palbociclib
 - Proportion of patients with temporary discontinuations
 - Time to dose reduction in number of days (from start of treatment) – 1st line treatment group only
 - Time to palbociclib discontinuation ('drug survival') in number of days (from start of treatment) in those patients permanently discontinuing palbociclib
 - Reasons for discontinuation.
 - 1st, 2nd, and 3rd line of treatment after progression: number of patients prescribed each medication, dose, and length of treatment.
- Description of the number of patients which are being prescribed as per posology of treatment.
 - Number of completed 28-day cycles per patient.
 - Proportion of patients co-administered letrozole at palbociclib initiation.
 - Proportion of patients co-administered fulvestrant at palbociclib initiation.

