Secondary Objective 2: To describe overall survival and progression-free survival, response (CR, PR), stable disease. This includes estimating the proportion of patients achieving those endpoints at 1, 2 and 3 years following palbociclib initiation; median survival, time to response and duration of response. In patients who respond to treatment, to describe PR and CR using "swimmer plots".

- Proportion of patients at 2-years following initiation of palbociclib who:
 - Are free from disease progression.
 - Are alive
 - Achieved PR
 - Achieved CR
 - Had stable disease
- Median (95% confidence interval [CI]):
 - PFS

PFIZER CONFIDENTIAL

- OS
 - Time to achieving best overall response
- Length of follow-up
- Best response to palbociclib, overall and by de novo and relapse status
- Time to best response – by de novo and relapse status
- Time to first response – overall and by de novo and relapse status

Secondary Objective 3: To describe the occurrence of neutropenia during the first-year post-initiation observation period.

- In the 6 months post-palbociclib initiation, proportion of patients who experience,
 - Neutropenia (overall and by grade, recorded and inferred from ANC measurements).
 - Worst neutropenia experienced within 3 months of palbo initiation
 - Febrile Neutropenia.

[figure not shown]
Secondary Objective 4: To describe the occurrence of gastro-intestinal toxicity, including diarrhoea, nausea and vomiting during the first-year post-initiation observation period.

- For each cycle, proportion of patients who experience Gastro-intestinal toxicity, including:
 - Diarrhoea.
 - Severity
 - Nausea.
 - Severity
 - Vomiting.
 - Severity
- Proportion of patients experiencing an AE during follow-up

Secondary Objective 5: To describe progression of clinical indicators, including biochemical and radiological indicators at each time-point available during the first year following palbociclib treatment initiation.

- Summary measures of full blood counts in the first 6 months following initiation:
 - Haemoglobin.
 - White cell counts.
 - Absolute neutrophil counts.
 - Platelet counts.
- Summary measures of liver function tests in the first 6 months following initiation:
 - aspartate transaminase (also called aspartate aminotransferase).
 - alanine transaminase (also called alanine aminotransferase).
 - alkaline phosphatase.
 - Albumin
 - Bilirubin

PFIZER CONFIDENTIAL

[figure not shown]

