Actual: Proportion of patients experiencing diarrhoea, nausea and vomiting as well as the associated grade were presented as categoric variables as per section 8.1.2. Proportion of patients experiencing an AE (at least one of neutropenia, diarrhoea, nausea, and vomiting) was presented as frequencies and proportions.

8.2.6 Secondary Objective 5: To describe progression of clinical indicators, including biochemical and radiological indicators at each time-point available during the first year following palbociclib treatment initiation (e.g., full blood counts, liver function tests, bone profile etc.).

Proposed: The first, mean, median, minimum, and maximum results per patient of all full blood counts, results of liver function tests and bone profile during the 6 months following palbociclib initiation will be summarised as quantitative variables (see section 8.1.1). For radiological indicators, proportions of patients with stable disease, progressive disease and who achieve CR/PR will be treated as binary variables (see section 8.1.3); the first or modal measurement will be used if there is more than one observation per patient. All the above will be assessed at 1, 15 and 22 days into the treatment cycle as well as after 1 year.

Actual: Baseline full blood counts, liver function tests, bone profile measurements and urea and electrolytes will be presented as quantitative variables as per section 8.1.1. To account for different number of test values in the 6 months post-palbociclib initiation, blood values were summarised per patient and then presented as quantitative variables as per section 8.1.1. Radiological indicators were presented as categoric variables as per section 8.1.2.

PFIZER CONFIDENTIAL

8.2.7 Secondary Objective 6: To describe BC-related healthcare resource utilisation (hospital admissions, outpatient visits and calls to CNS) during the first year following palbociclib initiation.

[figure not shown]

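### GI toxicity, the composite AE, and notes-recorded and febrile neutropenia have no on-palbociclib limit and inconsistent windows, so events on later treatment lines can enter these proportions

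*SAP*

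**What the plan says.** SAP 8.2.5 (Actual) reports GI toxicity as follows: "Proportion of patients experiencing diarrhoea, nausea and vomiting as well as the associated grade were presented as categoric variables as per section 8.1.2". For the composite it says "Proportion of patients experiencing an AE (at least one of neutropenia, diarrhoea, nausea, and vomiting) was presented as frequencies and proportions". Neither sentence gives a window or a link to treatment. The matching line in SAP 6 reads "Proportion of patients experiencing an AE during follow-up", under an objective confined to the first year.

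GI toxicity is described in four ways:
- **Per cycle:** Protocol 9.3 (days 1, 15 and 22 of each cycle) and SAP 6, "For each cycle, proportion of patients who experience Gastro-intestinal toxicity, including". SAP 8.2.5 (Proposed) also has this.
- **First year:** the objective itself, 8.2.5 (Proposed) and the row in SAP 8.2.9.
- **Over follow-up:** Protocol 9.7, "and gastro-intestinal toxicity including diarrhea, nausea and vomiting, during follow-up, will be presented".
- **Not stated:** SAP 8.2.5 (Actual).

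For neutropenia, SAP 6 puts both neutropenia and febrile neutropenia under a 6-month heading. SAP 8.2.4 (Actual) attaches 6 months to the ANC-inferred version and 3 months to worst grade. It does not clearly attach a window to neutropenia recorded in the notes, and gives none for febrile neutropenia. The SAP 8.2.9 row says first year.

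On follow-up, SAP 2.1 states: "The post-initiation observation period will be defined as the period from the index date until the end of the 3-year follow-up period". The period does not end at discontinuation; SAP 5.1 and 8.1 restrict the analysis to 2-year data. Protocol 9.3 records up to three lines of medication after palbociclib. The SAP does use an on-treatment definition elsewhere: "Concomitant medications (defined as medications prescribed whilst on palbociclib".

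**The concern.** Protocol 7 and SAP 2 say that the study should help readers understand palbociclib's safety in UK routine care and put US real-world safety evidence in context. On the unstated, first-year or follow-up wording, a patient who stops palbociclib at month 3, starts another line and vomits at month 8 counts in the GI proportion and the composite. A reader setting those figures beside other palbociclib data would take them as experience on the drug.

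SAP 8.2.9 also tabulates toxicity by treatment line. If lines leave palbociclib at different rates, a difference between them may partly reflect what was given afterwards.

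Protocol Annex 3, Table 1 lists each AE as an occurrence with dates and, except for febrile neutropenia, a grade; for example "AE: Diarrhoea (Y/N), date start and end, grade". It lists no causality field, so dates are the only listed means of separating palbociclib-era events from later ones. The SAP does not use them for this.

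**Working it through.** The study is descriptive, so there is no planned figure to reproduce. The check has three steps.

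**1. Text.**

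| Endpoint | Window(s) given | On-palbociclib limit |
|---|---|---|
| GI toxicity | per cycle; first year; follow-up; none | only through the per-cycle wording |
| Composite AE | follow-up (SAP 6); none (8.2.5 Actual) | none |
| Notes-recorded and febrile neutropenia | per cycle (Protocol 9.3); follow-up (Protocol 9.7); 6 months (SAP 6); first year (8.2.9); unclear or none (8.2.4 Actual) | none in the SAP |
| ANC-inferred neutropenia | 6 months | none, but short window |
| Worst neutropenia grade | 3 months | none, but short window |

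No passage ends a count at discontinuation or at the next line, or sets a window after the last dose.

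**2. Scope for misattribution.** Inputs: the median PFS figures in Protocol 7, namely 24.8 and 20.2 months (the two first-line letrozole trials) and 9.5 months (the second- or later-line fulvestrant trial). Assumptions: PFS stands in for time on palbociclib, and times are exponential with λ = ln 2 / median.

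Share off drug by month T = 1 − 2^(−T/median). Example: 1 − 2^(−12/24.8) = 28.5%.

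Off-drug share of a full window of length T = 1 − (1 − e^(−λT))/(λT).

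| Median (months) | Off drug by 3 / 6 / 12 / 24 months | Off-drug person-time, 3 / 6 / 12 / 24 months |
|---|---|---|
| 24.8 | 8.0 / 15.4 / 28.5 / 48.9% | 4.1 / 7.9 / 15.0 / 27.1% |
| 20.2 | 9.8 / 18.6 / 33.8 / 56.1% | 5.0 / 9.6 / 18.0 / 31.9% |
| 9.5 | 19.7 / 35.5 / 58.3 / 82.6% | 10.2 / 19.0 / 33.4 / 52.8% |

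Some patients counted as off drug have died and cannot contribute later events; stops for toxicity would add to the share.

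**3. From scope to inflation.** The endpoint is any event per patient, so someone who already had one on palbociclib cannot be added.
- *Neutropenia.* Protocol 7 gives 80.6% in pooled trial data, arising soon after initiation. If that rate applies and leaving is independent of it, at most 1 − 0.806 = 19.4% of leavers can be added. Over 12 months the ceiling is 0.194 × 28.5% = 5.5 points and 0.194 × 33.8% = 6.6 points for the first-line medians. Over 6 months it is 0.194 × 15.4% = 3.0 and 0.194 × 18.6% = 3.6 points.
- *Composite.* It contains neutropenia, so the same ceiling applies. Over 24 months it is 0.194 × 48.9% = 9.5 and 0.194 × 56.1% = 10.9 points.
- *GI events.* The documents give no rate. For illustration, assume a 12-month risk p on continuous palbociclib at constant hazard h = −ln(1 − p)/12, hazard r·h afterwards, and no deaths. The on-drug proportion is h/(h + λ) × (1 − e^(−12(h + λ))). With p = 30%, r = 1 and median 24.8: h = 0.0297 and λ = 0.0280, giving 25.7% on drug against 30.0% for any event, a gap of 4.3 points. Across p = 20% to 40% and r = 1 to 2, the 12-month gap is 2.9 to 11.3 points for the first-line medians and 6.5 to 21.0 points for 9.5 months. It is zero if r = 0, and smaller if events cluster early.
- *Febrile neutropenia.* At Protocol 7's 1.6% and about 200 patients (SAP 2.1), 3.2 cases are expected. Two later-line cases, as an illustration, would give 5.2/200 = 2.6%.

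**The case against.** A reader might infer that neutropenia and GI toxicity alike are counted from the index date through all of follow-up, with no link to treatment, and then reported as palbociclib toxicity. The documents do not support that.
- **Neutropenia is mostly windowed.** SAP 6 limits it to 6 months, as does the ANC-based analysis; worst grade stops at 3 months. This stands, and leaves only the 8.2.4 (Actual) wording for the notes-recorded and febrile versions.
- **GI toxicity has a cycle link.** SAP 6 specifies it per cycle and says its list reflects what was done; 8.2.5 (Actual) may simply be silent about the window. This stands as a reason not to assert that GI events were counted through follow-up. It does not settle which analysis was reported, and it does not cover the composite.
- **The objectives describe occurrence, not causation.** Protocol 9.9 disclaims definitive causal conclusions and SAP 8.2.8 plans no safety analyses. Counting from initiation is a legitimate descriptive choice. Even so, Objectives 3 and 4 tabulate toxicity in a study whose stated purpose includes palbociclib safety, so the two kinds of event should be distinguishable.
- **Off-drug time is not bias.** This stands, as step 3 of the working shows.
- **The subgroup effect is not shown.** It is tempting to say that second-line figures are inflated most. Earlier deaths would shorten off-drug observation, later lines need not be more toxic, and the subgroup's size is not given. The 9.5-month median comes from a fulvestrant combination, whereas the programme targeted previously untreated disease with an aromatase inhibitor.

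**Conclusion.** The point holds for GI toxicity as worded in SAP 8.2.5 (Actual), for the composite AE, and for notes-recorded and febrile neutropenia as worded in 8.2.4 (Actual). Their windows conflict between sections, and no stated rule separates events on palbociclib from events after it. Events on later lines can therefore enter these proportions, overall and by treatment line. A first-year cap alone would not remove them.

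Under the PFS-proxy and exponential assumptions, 28.5% to 58.3% of patients are off palbociclib by 12 months and 15.4% to 35.5% by 6 months; the upper ends bear only on the second-line subgroup. The resulting inflation cannot be fixed from the documents. For notes-recorded neutropenia it is probably a few points. For GI events it depends on rates that are not given. For febrile neutropenia a couple of cases would matter.

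This should be corrected before the figures are set beside other palbociclib safety data. It does not affect the primary objective.

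**What to change.** In SAP 6, 8.2.4 and 8.2.5, with the 8.2.9 rows aligned:
1. State one window per endpoint: first year for GI toxicity and the composite; the existing 6 months for neutropenia (notes-recorded, febrile and ANC-inferred) and 3 months for worst grade. The neutropenia windows should not be lengthened.
2. Within that window, count an event as on-palbociclib only if it starts between the index date and permanent palbociclib discontinuation plus a stated lag. A lag of 28 days is one option; it is an analysis choice without a basis in the documents and can be varied as a sensitivity check.
3. Show events that start later in a separate row labelled as after palbociclib, so that nothing is lost.
4. Say whether the per-cycle GI analysis in SAP 6 was carried out.

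Cost: SAP wording, one date filter and a rerun of the affected tables. Protocol Annex 3, Table 1 already lists AE start dates and the palbociclib end date, so no new data are needed. A few delayed events will move to the separate row. Events or discontinuations with dates imputed under SAP 7 need a flag, because an assumed mid-month or mid-year date can put an event on the wrong side of the cut.

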7. RATIONALE AND BACKGROUND

BC is the most frequently occurring cancer in women and is a major public health problem, with 1.7 million new cases diagnosed globally in 2012, representing 25% of all incident cancer cases (1). In Europe, more than 464,000 new cases of BC were diagnosed in 2012. The UK incidence rate is the sixth highest in Europe, with around 54,900 new BC cases every year (2). HR+ BC represents the largest therapeutic subtype of the disease and accounts for over 80% of cases in the UK (4).

Annually, approximately 6-7% of new BC cases present as *de novo* metastatic disease and approximately 30% of women with early BC go on to develop metastatic disease (2). Survival from BC largely depends on the stage at diagnosis; the 1-year survival is 100% for patients diagnosed at stage I, versus 63% for patients diagnosed at stage IV; and five-year survival is 99% and 15% respectively for stage I and IV (5,6).

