- Summary measures of bone profile in the first 6 months following initiation:
 - Calcium.
 - Phosphate.
- Summary measures of urea and electrolytes in the first 6 months following initiation:
 - Creatinine
 - Potassium
 - Sodium
 - Urea
- Summary measures of radiological indicators in the first 6 months following initiation including the proportion of patients with:
 - Stable disease.
 - Progressive disease.
 - CR or PR.

Secondary Objective 6: To describe BC-related healthcare resource utilisation during the first year following palbociclib initiation.

- Summary measures of hospital admissions for each line of therapy, including:
 - Proportion of patients with at least one inpatient admission recorded
 - Inpatient admissions per patient.
 - Elective or non-elective.
 - Reasons for admission (including day cases).
 - Length of stay per inpatient admission.
 - Proportion of patients with at least one outpatient visit recorded
 - Outpatient visits per patient.
 - Reason for outpatient visit
 - Type of HCP seen during outpatient visits
- Proportion of patients with at least one interaction with CNS
- Number of CNS interactions per patient
- Type of CNS interaction
- Reason for CNS interaction
- Proportion of patients with at least one interaction with AOS
- Number of AOS interactions per patient
- Type of AOS interaction
- Reason for AOS interaction

For the estimation of endpoints, *the following definitions will be implemented. PFS will be defined as the time from the date of palbociclib initiation to the date of first documented disease progression (as documented in the radiological assessment section of the eCRF) or death. OS will be defined as the time from the date of palbociclib initiation until death from any cause. Time to achieving best overall response will be defined in patients who respond to treatment as the time from the date of palbociclib initiation until*

PFIZER CONFIDENTIAL

achievement of the best overall response: CR, or PR if CR is not achieved during follow-up. Duration of response will be defined as the time from the date CR or PR was first documented (whichever is recorded first) to the date of first documented disease progression or death from any cause (whichever occurs first).

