8.1.1 Analysis for quantitative data

Quantitative data will generally be analysed using basic summary statistics of central tendency (including means and medians) and dispersion (including standard deviations, the interquartile range [IQR] and the range). If distributions are normally distributed (evaluated through inspection of histograms), 95% confidence intervals will be calculated assuming a normal distribution, otherwise the median and IQR will be presented instead. Where appropriate, i.e., for ordinal endpoints frequency and percentages will be presented along with summary statistics.

PFIZER CONFIDENTIAL

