Proposed: The total number of inpatient, emergency department visits and outpatient visits will be calculated in the first year palbociclib initiation. The number of visits to each of these clinics per patient will be summarised as a quantitative variable (see section 8.1.1). Reasons for admission for each of these will be compiled and treated as a categorical variable (see section 8.1.2). For inpatient admissions, the proportion of visits that were planned/elective or non-elective/accident and emergency will be described using frequencies and percentages (see section 8.1.3). Length of stay per inpatient admission will be treated as a quantitative variable (see section 8.1.1). The number of phone calls to CNS will be compiled with the distribution of reasons analysed as a categorical variable (see section 8.1.2). The number of contacts with the AOS with distributions of reasons and types of contact (phone calls or visits) will also be compiled and displayed using a frequency table with percentages (see section 8.1.2).

Actual: Proportion of patients with at least one inpatient admission, reasons for admission, elective or non-elective admission were presented as a categoric variable as per section 8.1.2. Inpatient, outpatient, CNS and AOS interactions per patient as well as length of inpatient admission were presented as per quantitative variables as per section 8.1.1. All other endpoints were presented as categoric variables as per section 8.1.2.

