Summary measures of hospital admissions for each	Full Analysis set	Secondary objective 6	Overall and Treatment Line	Frequency and percentages of inpatient, outpatient and emergency department visits	Excluded

PFIZER CONFIDENTIAL

line of therapy				and summary measurements of visits per patient (incl. Mean/Median/SD/IQR/Range) and lengths of inpatient stay	
Summary of phone calls from patient to Cancer National Services	Full Analysis set	Secondary objective 6	Overall and Treatment Line	Frequency and percentages for phone calls and reasons for visit	Excluded
Summary of phone calls from patient to Acute Oncology Services	Full Analysis set	Secondary objective 6	Overall and Treatment Line	Frequency and percentages for phone calls, reasons for visit and contact types	Excluded

PFIZER CONFIDENTIAL

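### First-year resource use is reported only as counts per patient, with no observed time, so use is understated for patients lost or discharged early and the counts cannot be read as annual rates.

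*SAP*

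**What the plan says.** SAP 8.2.7 sets the window: "The total number of inpatient, emergency department visits and outpatient visits will be calculated in the first year palbociclib initiation". The Proposed paragraph then says "The number of visits to each of these clinics per patient will be summarised as a quantitative variable". The Actual paragraph keeps the same form: "Inpatient, outpatient, CNS and AOS interactions per patient as well as length of inpatient admission were presented as per quantitative variables". The hospital-visit row of the table in SAP 8.2.9 asks for "summary measurements of visits per patient (incl. Mean/Median/SD/IQR/Range) and lengths of inpatient stay" in the full analysis set, overall and by treatment line. SAP 6 introduces the endpoint as "Summary measures of hospital admissions for each line of therapy, including".

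The method behind all of these is SAP 8.1.1: "Quantitative data will generally be analysed using basic summary statistics of central tendency (including means and medians) and dispersion". It contains no rate and no person-time denominator.

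Follow-up is unequal by design. SAP 2.1 says "Patients will contribute data up to the time that they are lost to follow-up (for example due to discharge, death, or other reasons" or until three years after the index date.

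Three nearby provisions do not reach this objective:

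- Length of follow-up is an endpoint, but under Secondary Objective 2 only (SAP 6 and 8.2.3).
- The censoring rules at the start of SAP 8.2 concern survival, progression and response.
- Protocol 9.9 recognises attrition bias, but the remedy it names is Kaplan-Meier estimation of PFS, OS, CR and PR, which does nothing for visit counts.

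**The concern.** A patient lost or discharged at month 3 supplies three months of visits and still counts as one whole patient in the denominator. The later visits are not flagged as missing. The recorded count looks like a complete, low count, so the rule of excluding missing data (SAP 7 and the last column of 8.2.9) does not catch it.

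Two things follow. First-year use is understated to the extent that patients leave observation alive. Separately, a reader who takes the mean as visits per year of treatment or of life reads too low a figure, because the time behind it is not shown. Both matter more when results are laid out by treatment line, since nothing in the tables shows whether the lines were observed for similar lengths of time.

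**Working it through.** **1. Plan's own figure.** The documents give no resource-use estimate and no loss or death rate for this cohort, so there is nothing to reproduce. What follows is illustrative.

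**2. Who can have a short first year.** Initiation ran from April to December 2017, and first data collection was expected between November 2018 and February 2019, with later updates (SAP 2 and 2.1). The shortest gap is December 2017 to November 2018, about 11 months. The longest is April 2017 to February 2019, about 22 months. A first year cut short only by the timing of data collection should be rare. Death, discharge and true loss remain.

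**3. Relation between the two summaries.** Let N be the number of patients and T each patient's observed time within year 1, at most 1 year.

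- Mean count per patient = total events / N.
- Rate per patient-year = total events / total T.
- Ratio of the first to the second = total T / N = mean observed time.

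This is an identity and needs no assumption about visit rates. The mean count can never exceed the rate.

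**4. Size under assumed attrition.** Let S be the proportion still observed at 1 year, with exponential time to death or loss. Mean observed time = (1 − S) / (−ln S). The last column takes an arbitrary 12 visits per patient-year.

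| S (assumed) | Calculation | Mean observed years | Mean count below rate | Mean count |
|---|---|---|---|---|
| 0.95 | 0.05 / 0.0513 | 0.975 | 2.5% | 11.7 |
| 0.90 | 0.10 / 0.1054 | 0.949 | 5.1% | 11.4 |
| 0.85 | 0.15 / 0.1625 | 0.923 | 7.7% | 11.1 |
| 0.80 | 0.20 / 0.2231 | 0.896 | 10.4% | 10.8 |

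**5. How much of that gap is missed use.** Take S = 0.80 and a constant visit rate.

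- All attrition is death: true mean first-year use is 12 × 0.896 = 10.8, equal to what is recorded. Missed use is 0%.
- All attrition is loss of patients who live through the year: true use is 12.0 and recorded use is 10.8. Missed use is 10.4%.

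The gap in step 4 is therefore an upper limit on the understatement of first-year use under these assumptions. Its position between the two ends depends on the split between loss and death, which the documents do not give.

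**6. Are early deaths low users?** One million patients were simulated per scenario with S = 0.90 (deaths only), a base of 12 visits per year, and a raised rate in the last 3 months before death. Mean first-year visits among those who died were 5.9 with no rise, 8.5 with a 2-fold rise, 11.1 with a 3-fold rise and 13.7 with a 4-fold rise. Survivors averaged about 12. The direction is not assured.

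**The case against.** The strongest reply is that the objective asks for use during the first year after initiation, not for a rate. A patient who dies at month 3 has no later use, so the count to death is complete. For deaths, the mean per patient is then the correct mean use per patient started on treatment. This stands. A reader might infer that early deaths drag annual use down as artificial low users. The documents do not support that: nothing is missing for those patients, and step 6 shows that they need not be low users.

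A second reply is that the arithmetic concerns means, whereas SAP 8.1.1 turns to the median and IQR when data are not normal, and medians of skewed counts need not move. This also stands, although SAP 8.2.9 lists the mean as well.

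A third is that attrition is acknowledged and length of follow-up is reported. That is true, but neither is connected to resource use, so a reader cannot recover the observed time behind these tables, least of all by line.

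A fourth is that this is a descriptive secondary objective with no hypothesis or decision attached (SAP 4.1 and 4.2). That limits the weight of the point. It does not remove the undercount for patients lost or discharged alive.

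**Conclusion.** The point holds in a limited form. The counts understate first-year use for patients lost or discharged before 12 months. They cannot be read as annual rates, overall or by treatment line. For patients who die, only the rate per year alive differs.

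The size in this cohort is unknown. With exponential attrition and 80% to 95% still observed at 1 year, both assumed, the mean count lies about 10% to 2.5% below the rate per patient-year. Only the share due to loss is missed use.

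Two larger figures are tempting and should not be used. Protocol 7 gives 1-year survival as "versus 63% for patients diagnosed at stage IV". Put into the same formula, 0.63 gives 0.37 / 0.462 = 0.801 and a gap of about 20%. But that is a background figure for stage IV disease in general, not for patients on palbociclib. Protocol 7 itself cites first-line median PFS of 20.2 and 24.8 months. Under an exponential curve these imply 1-year PFS of 0.5^(12/20.2) = 66% and 0.5^(12/24.8) = 72%, and survival cannot be lower than PFS.

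A reader might also set 90% retention in one treatment line against 63% in another and infer a spurious difference of 1 − 0.801/0.949 = 15.6%. The documents give no retention by line and plan no formal contrast between lines, so that figure rests on invented inputs.

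**What to change.** Keep the counts per patient. In SAP 8.2.7 and 8.2.9, add the following for inpatient, emergency, outpatient, CNS and AOS contacts, overall and by treatment line:

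- total observed time, running from the index date to the earliest of 12 months, death or last contact;
- events per patient-year, as total events over total observed time, with a 95% CI that allows for between-patient variation (for example a negative binomial model with log observed time as offset, or a bootstrap that resamples patients);
- the number who died and, separately, the number lost or discharged before 12 months.

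State in 8.2.7 that the count per patient describes use recorded in the first year and is complete for patients who died but not for those lost. Label the rate as use per year alive and observed, so that it is not taken for mean first-year use per patient started.

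The cost is one or two extra columns per table. Dates of death and of the last clinic or hospital visit are already in the dataset (Protocol 9.3 and the SAP appendix). The columns can also be added to outputs already produced.
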